## **Aim of the study:**

1-To evaluate the efficacy of antibodies cocktail (casirivimab and imdevimab) compared to standard antiviral therapy in reducing 28-day mortality in hospitalized patients with moderate, severe or critical COVID19

2-To evaluate safety of antibodies cocktail (casirivimab and imdevimab) compared to standard antiviral therapy by monitoring of hypersensitivity and infusion related reactions or other significant adverse effects

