## **Outcomes:**

Parameters that will be assessed during hospitalization at day 0(baseline), day 3, 7, 14, 28 include:

- C-reactive protein (CRP)
- ferritin
- lactate dehydrogenase (LDH)
- D-dimer
- serum creatinine(S.Cr) and estimated creatinine clearance(CrCl)
- alanine aminotransferase (ALT), aspartate aminotransferase (AST), albumin, bilirubin

Clinical outcomes measured before & during intervention

1) Primary outcomes

- 1- 28-days mortality rate (efficacy).
- 2-PCR test results at end of hospital visit (efficacy).
- 3-precentage of patients who developed infusion related or hypersensitivity reactions during and after the end of drug infusion and reporting of any Serious and unexpected adverse events may occur that have not been previously reported with REGEN-COV use that may cause drug discontinuation (Safety).

2) Secondary outcomes

- 1-Need for invasive mechanical ventilation.
- 2- Invasive mechanical ventilation and oxygen support duration (days).
- 3- Time to clinical improvement (defined as 2 points reduction in the WHO disease ordinal progression scale(11&12) or discharge, whatever happens first)
- 4- ICU and hospitalization length of stay (days).
- 5- SOFA score(13) on day 0,3,7,14, and 28.
- 6- COVID19 WHO disease progression score(11&12) from day 0 to day 28.
- 7- Inflammatory markers including CRP, ferritin, LDH
- 8- liver and kidney functions

In addition to clinical outcomes measured before and during intervention, Vital signs, glasgow coma score (GCS),complete blood count (CBC), artierial blood gas (ABG) and prothrombin time (PT) is recorded at day0.

Patients' charactrestics(age,gender) and relevant medical and medication history and current COVID-19 treatment drugs will be recorded on admission

Duration of research will be about 6 months from Novmber 2021 to March 2022

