## **Statistical Analysis Plan (SAP):**

Intention-to-treat strategy will be used in this study. Intention-to-treat strategy will be used in this study. Statistical analysis will be achieved with SPSS, version 26.

Categorical variables will be presented as proportion and percent. Continuous variables will be presented as mean (standard deviation) for parametric data or as a median (25th-75th percentile) for non-parametric data.

Regarding baseline characteristics, Kruskal-Wallis or ANOVA test (depending on type of data and the continuous data distribution (normal or not)) will be used to compare these characteristics between the study groups. We will report the P-value for our statistical tests with level of statistical significance will be P-value  $\leq 0.05$ .

In case of existing differences in some baseline characteristics, logistic regression will be performed. This allows studying the effect of these variables on the primary outcomes of the study to exclude the effect of these confounding variables and to ensure the effect on the outcomes is due to interventions.

Regarding the outcomes, we will compare the 28-day all-cause mortality rate, result of PCR test at hospital discharge and incidence of infusion related or hypersensitivity reactions during and after the end of drug infusion (primary outcome) using the Kruskal-Wallis test with reporting the P-value.

While the secondary outcomes (hospital stay duration, icu stay duration and others) are compared using Kruskal-Wallis or ANOVA test depending on type of data and the distribution of data (normal or not)

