## **Sample Size:**

A total sample sizes of 246 patients would achieve at least 80 % power to detect a risk difference of 0.2 (20%) in the 28-day all-cause mortality (primary outcome) with a significance level ( $\alpha$ ) of 0.05 and 95% confidence level using the ANOVA or Kruskal-Wallis test of independent proportion in G\*Power software. To compensate for the estimated loss-to-follow-up and increase the study power, we will increase the sample size in both remdesivir and favipravir groups to be 106 patients compared to 53 patients in Antibodies cocktail Group As Antibodies cocktail product is available for only about 50 COVID-19 patients. In addition, the ratio (1:2:2) is the closest to reality according to number of patients who receive each drug.

The mortality data was estimated from the average mortality in August, September, and October 2021 at the Mansoura University Isolation Hospital among all hospitalized patients. Mortality rate is found to be about 360 cases in these 3 months (120 cases / month). The online system has been used to obtain mortality rate in these three months.

The current admission rate at the Mansoura University – Isolation Hospital is 250 cases per month on average; our needed sample is about 250 cases.

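### Mortality and discharge PCR are both primary efficacy outcomes, each tested at 0.05 with no rule for which decides; the chance of at least one false-positive primary efficacy test is about 10%, not 5%

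*Combined protocol and SAP*

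**What the plan says.** The Outcomes section numbers three primary outcomes. The first is "1- 28-days mortality rate (efficacy"), the second "2-PCR test results at end of hospital visit (efficacy"). The third is the percentage of patients with infusion-related or hypersensitivity reactions, together with serious and unexpected events "that have not been previously reported with REGEN-COV use that may cause drug discontinuation (Safety").

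The SAP compares mortality, the PCR result and reactions between the groups as "primary outcome) using the Kruskal-Wallis test with reporting the P-value". One threshold serves every test: "We will report the P-value for our statistical tests with level of statistical significance will be P-value" of 0.05 or less. The combined document contains no multiplicity adjustment, no testing order and no success rule.

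Two other sections treat mortality as the outcome that matters. Under Aim of the study, the efficacy aim is to assess the antibody combination "in reducing 28-day mortality in hospitalized patients"; PCR is not mentioned there. Under Sample Size, the 20% risk difference to be detected at alpha 0.05 is "in the 28-day all-cause mortality (primary outcome"), in the singular.

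**The concern.** Two outcomes labelled efficacy have equal primary status and each gets the full 0.05. If mortality shows nothing and PCR gives P = 0.03, the plan allows a report that a primary efficacy outcome was met. The 5% error rate assumed in the sample size then no longer describes the trial's efficacy claim, and a virological measure can carry a conclusion that the aim frames in terms of survival.

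PCR is also poorly placed to carry that claim alone. The Outcomes section times it at the end of the hospital visit and the SAP at hospital discharge, and neither says how a patient who dies in hospital is counted. If deaths are dropped, the comparison is among survivors only, a group that treatment may itself alter.

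**Working it through.** **Inputs from the document.** Two primary efficacy outcomes and one primary safety outcome (Outcomes); 0.05 for each test, three-group Kruskal-Wallis (SAP); 246 patients, at least 80% power, alpha 0.05, mortality only (Sample Size); groups of 53, 106 and 106 (Sample Size and Table 2).

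**Step 1. The plan's own figure.** A one-way ANOVA with three equal groups, alpha 0.05 and 0.2 entered as Cohen's f has noncentrality 246 × 0.2² = 9.84 on 2 and 243 degrees of freedom. Power is 80.4%, and 246 is the first multiple of three to reach 80%. So 246 reproduces with all of the 0.05 spent on mortality and nothing set aside for PCR. (Whether 0.2 as an effect size f is the same as a 20% risk difference is a separate matter and does not affect the error-rate arithmetic.)

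**Step 2. Error rate over the two efficacy outcomes.** Assume no true difference between groups on either outcome.
- Independent tests: 1 - (1 - 0.05)² = 1 - 0.9025 = 9.75%.
- Upper bound under any dependence: 0.05 + 0.05 = 10%.
- If mortality alone decides: 5%.

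**Step 3. Effect of correlation.** The document gives no correlation between death and PCR result. The planned test was simulated on binary outcomes at 53/106/106 with assumed event rates of 48% and 30% (40,000 runs for each setting).

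| Latent correlation | At least one false-positive efficacy test |
|---|---|
| 0 | 9.7% |
| 0.3 | 9.7% |
| 0.6 | 9.3% |
| 0.9 | 8.9% |

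Even strong correlation removes little of the inflation.

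**Step 4. What the figure counts.** The three-group test has no direction. It can reject because remdesivir and favipiravir differ, or because the antibody group does worse. Simulating the null with independent outcomes and assumed event rates of 30% to 50%, rejection with the antibody group having the lowest event rate occurs in about 1.8% of trials for one outcome and about 3.5% for either of two. The doubling remains; the absolute level is lower.

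**Step 5. Power cost of sharing alpha.** Assume control mortality of 120/250 = 48%, from the monthly deaths and admissions under Sample Size. The document does not state this rate, and enrolled patients may differ. Take 28% on the antibody, with 53 against 106 patients.
- Pooled rate: (53 × 0.28 + 106 × 0.48)/159 = 0.4133.
- Standard error under the null: √[0.4133 × 0.5867 × (1/53 + 1/106)] = 0.0828.
- Standard error under the alternative: √[0.28 × 0.72/53 + 0.48 × 0.52/106] = 0.0785.
- Power at 0.05: Φ[(0.2 - 1.960 × 0.0828)/0.0785] = 68%.
- Power at 0.025: Φ[(0.2 - 2.241 × 0.0828)/0.0785] = 57%.

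For the three-group test at 53/106/106, with both comparators at 48%, the corresponding values are 65% and 54%.

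**The case against.** The best defence is that the document already points to mortality. It is listed first among the primary outcomes, it is the only efficacy aim, and it is the only outcome used for sizing. On that view the plan lacks a sentence rather than a strategy. This stands in part: it shows which outcome the sponsor appears to intend and makes the repair easy. It does not settle the matter, because no section says that mortality decides, and the Outcomes section and the SAP give PCR equal standing.

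A reader might go further and count all three primary outcomes, giving 1 - 0.95³ = 14.3% as the chance of a false primary success. The document does not support that. The third outcome is labelled safety, and a difference in reactions is not an efficacy success. Nor is its null hypothesis credible: under Interventions, favipiravir is given orally or by tube, so a reaction to infusing the study drug cannot occur in that group. Even as the chance of any false-positive primary test, 14.3% assumes independence; the upper limit is 15%.

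It is equally tempting to read 9.75% as the chance of falsely declaring the antibody effective. Step 4 shows that it is not.

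Finally, fixed-sequence testing is one valid rule among several. That is correct. It is preferred here because it follows the stated aim and sizing and leaves mortality at 0.05.

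**Conclusion.** The concern holds for the two efficacy outcomes. With mortality and PCR each tested at 0.05 and no decision rule, the chance of at least one false-positive primary efficacy test is 9.75% under independence, 8.9% to 9.7% over the correlations simulated, and at most 10%, against the 5% used for sizing. This assumes no true group difference on either outcome and counts a difference in any direction among the three groups. It leaves out any later pairwise comparisons and any choice between unadjusted results and the logistic regression that the SAP adds when baseline characteristics differ; the plan sets no rule for either. The point should be corrected before analysis, since the plan as written lets PCR alone support a primary efficacy claim.

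**What to change.** Amend the Outcomes section and the SAP as follows.

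1. Name 28-day all-cause mortality as the single primary efficacy outcome, tested at 0.05.
2. Make the PCR result the first secondary outcome, tested formally only if mortality is significant. Use one definition of its timing in both sections and state how in-hospital deaths count.
3. Report infusion and hypersensitivity reactions as safety, by group, with risk differences and 95% confidence intervals, and not as a further test of success.

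The cost is a few sentences and the loss of a stand-alone primary claim on PCR. Sample size is unaffected, because mortality keeps the 0.05 on which the study was sized.

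If PCR must stay co-primary, Holm's procedure at an overall 0.05 would control the error rate. It is less attractive: mortality is then tested at 0.025 unless PCR has already been declared significant. Under the assumed 48% against 28% with 53 and 106 patients, power for mortality at that level is about 57% instead of 68%.

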**Figure 2: Assignment of the included COVID cases at their groups.**

**Figure 3: Frequency of interventions in included patients**

## **Method:**

The type of this study is single blind non-RCT and is considered a Phase IV Clinical trial (post-marketing study) to report efficacy and safety of new medicine.

We use PubMed search tool to find clinical studies that performed to test efficacy and safety of developed immunotherapy in treatment of COVID-19 with about 4,000 results with focusing on antibodies developed as antiviral against COVID-19 obtaining only 70 results from which REGN-COV2, a Neutralizing Antibody Cocktail is selected with its only one clinical study up to now (REGN-COV2, a Neutralizing Antibody Cocktail, in Outpatients with Covid-19) which is published in New England Journal of Medicine on January 21, 2021.

Another resource used to obtain data is Fact Sheet for Health Care Providers-EUA OF casirivimab and imdevimab which provides clinical data about the use of this antibodies cocktail. Endnote citation software is used for citation of references.

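### Repeated secondary outcomes (SOFA, CRP, ferritin, LDH, liver and kidney function) are to be compared with no baseline covariate, although day 0 values are collected and the study is described as non-randomised

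*Combined protocol and SAP*

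**What the plan says.** The Outcomes section lists as secondary outcomes "SOFA score(13) on day 0,3,7,14, and 28", "Inflammatory markers including CRP, ferritin, LDH" and "liver and kidney functions". The laboratory schedule is introduced with "Parameters that will be assessed during hospitalization at day 0(baseline), day 3, 7, 14, 28 include". Each of these outcomes therefore has a day 0 value and up to four later values.

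The SAP covers all secondary outcomes in one sentence: "While the secondary outcomes (hospital stay duration, icu stay duration and others) are compared using Kruskal-Wallis or ANOVA test". The choice between the two tests depends on the type and distribution of the data. The sentence names no baseline covariate, change from baseline, repeated-measures model or analysis day.

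The SAP plans one adjustment: "In case of existing differences in some baseline characteristics, logistic regression will be performed". Its purpose is given as "This allows studying the effect of these variables on the primary outcomes of the study".

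On allocation, the Method section states: "The type of this study is single blind non-RCT". The Population section says that patients will be randomised 2:1:1 to the three groups, while the Interventions section gives 1:2:2, which matches the group sizes 53/106/106 in Table 2.

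**The concern.** The SAP accepts that baseline differences can confound the comparison, but it acts on this only for the primary outcomes, and only if differences are found. Logistic regression would not in any case serve continuous outcomes such as CRP or SOFA.

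Enrolment runs from moderate to critical disease. The Sample Size section ties the group sizes partly to cocktail supply and to how many patients receive each drug in practice, which reads like routine-care allocation. Day 0 severity could then differ between groups. Part of any such difference would reappear at follow-up and could be read as a drug effect on inflammation or organ function. Even without systematic imbalance, leaving out the day 0 value discards precision that the collected data already offer.

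**Working it through.** **The plan's own figure.** The documents give no figure for the secondary outcomes. The only sizing figure, 246, concerns mortality. It reproduces as a three-group one-way ANOVA with Cohen f = 0.2, alpha 0.05 (power 0.804), and has no bearing on this point.

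**Inputs.** Group sizes 53/106/106 come from Table 2 and Sample Size, and the 0.05 level from the SAP. Three inputs are assumptions, because the documents give none of them: the day 0 shift in group A (d = 0.3 or 0.5 SD), the baseline-to-follow-up correlation (r = 0.5 or 0.7), and the number still measured at a late visit (20/40/40). There is no drug effect throughout.

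**Step 1: carry-over.** If follow-up depends on group only through the day 0 value, the false difference at follow-up is r × d: 0.5 × 0.3 = 0.15 SD up to 0.7 × 0.5 = 0.35 SD.

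**Step 2: false-positive rate of the unadjusted test.** The noncentrality is λ = [n_A × n_(B+C) / N] × (r × d)².
- All patients: 53 × 212 / 265 = 42.4, so λ = 42.4 × (r × d)², F with 2 and 262 df.
- 20/40/40: 20 × 80 / 100 = 16, so λ = 16 × (r × d)², F with 2 and 97 df.

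| d | r | λ (265) | ANOVA, 265 | ANOVA, 20/40/40 |
|---|---|---|---|---|
| 0.3 | 0.5 | 0.954 | 12.8% | 7.7% |
| 0.3 | 0.7 | 1.870 | 21.1% | 10.5% |
| 0.5 | 0.5 | 2.650 | 28.5% | 13.0% |
| 0.5 | 0.7 | 5.194 | 51.5% | 21.6% |

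Simulation of 4,000 null trials per row at full size agrees: ANOVA 12.7%, 22.0%, 28.6% and 51.3%; Kruskal-Wallis 12.1%, 21.5%, 26.4% and 48.7%. At a weaker correlation, r = 0.3, the formula gives 7.6% (d = 0.3) and 12.8% (d = 0.5).

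**Step 3: adding the day 0 value, same model.** Simulated ANCOVA rejects 5.3%, 4.8%, 5.1% and 5.3% in the four rows.

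**Step 4: a less favourable model.** Let group A be shifted by d at day 0 and equally at follow-up, a stable difference in severity. Unadjusted, λ = 42.4 × d² = 3.816 or 10.6, so the test rejects 39% or 83% of the time. After adjustment the remaining standardised shift is d(1 − r)/√(1 − r²):

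| d | r | remaining shift | λ | ANCOVA rejects |
|---|---|---|---|---|
| 0.3 | 0.5 | 0.173 | 1.272 | 15.6% |
| 0.3 | 0.7 | 0.126 | 0.673 | 10.4% |
| 0.5 | 0.5 | 0.289 | 3.533 | 36.8% |
| 0.5 | 0.7 | 0.210 | 1.871 | 21.1% |

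**Step 5: if allocation is truly random.** All tests stay near 5% on average. Chance imbalance for A versus B and C combined has standard error √(1/53 + 1/212) = 0.15 SD. Adjustment leaves 1 − r² of the residual variance: 0.75 at r = 0.5 and 0.51 at r = 0.7, so 25% to 49% could be removed.

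**Step 6: a conditional trigger.** A true 0.3 SD day 0 shift has λ = 3.816, so the planned baseline ANOVA would reach p ≤ 0.05 only about 39% of the time. Extending the existing trigger to these outcomes would miss most such imbalances.

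**The case against.** Several stronger readings are tempting, and the documents do not support them.

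- *The SAP compares raw follow-up values.* It does not say so. Unadjusted comparison is the plain reading of ANOVA or Kruskal-Wallis by group, but the analysis variable and day are not specified. Change scores would not be a safe reading either. In the model of Steps 1 to 3, with d = 0.5, they reject 29% (r = 0.5) and 19% (r = 0.7) of the time. They stay near 5% only under the stable shift of Step 4.
- *A baseline difference passes through in full.* In the main model only a fraction r does, and the rates in Step 2 already reflect that.
- *Baseline adjustment restores 5%.* This holds only if the groups differ through the measured day 0 value alone. Step 4 shows a case where it does not.
- *The study is certainly non-randomised.* The Population section says otherwise. The Method and Sample Size sections favour the non-random reading, but the conflict is not resolved in the documents.
- *About 40 tests are planned.* One can count SOFA on 4 days, three inflammatory markers × 4 and six liver and kidney measures × 4: 4 + 12 + 24 = 40, with 40 × 0.05 = 2 false positives expected if every null holds. The Outcomes section sets a measurement schedule, however, and nothing plans a test on each day. The count applies only if each day is tested separately.

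It is also fair to object that the full-size rates ignore attrition. The tests are done during hospitalisation, and 120 deaths per 250 admissions a month would be about 48% mortality. The 20/40/40 column shows lower error rates for that reason, but selection through death and discharge is a further bias that baseline adjustment does not address. Finally, these are secondary outcomes, and a mixed model is one of several acceptable analyses.

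None of this removes the omission. In every imbalance scenario tried, the unadjusted test did worse than the baseline-adjusted one.

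**Conclusion.** The point holds, and the change should be made, though it does not touch the primary analysis. For the repeated secondary outcomes no baseline covariate is planned, and the SAP's one adjustment does not reach them.

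If group A differs at day 0 by an assumed 0.3 to 0.5 SD, with r = 0.5 to 0.7 and no drug effect, the false-positive rate is about 13% to 51% with all 265 measured and about 8% to 22% with 20/40/40. Adjustment brings it to about 5% if the groups differ only through the day 0 value. If they differ stably in severity, it falls from about 39% to 83% to about 10% to 37% (all 265 measured), so the bias is reduced and may not be removed. Under true randomisation the issue is mainly lost precision. The imbalances, correlations and late-visit numbers are all assumptions; the omission itself is in the text.

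**What to change.** For each repeated marker, prespecify a linear or linear mixed model, on the log scale for skewed markers, with group, day, group-by-day, the marker's own day 0 value and named baseline severity variables. Fit it regardless of any baseline p-value. Report cocktail-versus-standard differences with 95% confidence intervals. State that the results apply to patients alive and still measured at each day, and that residual confounding may remain if allocation is not random. If each day is to be tested separately, say so and address the number of tests.

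Reconcile the Population and Method sections on whether patients are randomised, and the Population and Interventions sections on the ratio.

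The cost is SAP wording and some extra analysis in SPSS, which is already the planned software. No new data are needed.

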### **Inclusion criteria**

Patient should fulfill all this characteristics to be included:

1-age more than 12 years old.

2-weight not less than 40 kg.

3-Moderate, sever or critical COVID-19 disease as defined by WHO.

4-PCR- confirmed patients to be Positive before inclusion.

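### The plan does not say how patients who die are counted in hospital stay, ICU stay and time to clinical improvement, although it implies that deaths are common

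*Combined protocol and SAP*

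**What the plan says.** The Outcomes section lists, among the secondary outcomes, "ICU and hospitalization length of stay (days" and time to clinical improvement, defined as "2 points reduction in the WHO disease ordinal progression scale(11&12) or discharge, whatever happens first". Neither entry mentions death, and the improvement definition does not say that discharge means discharge alive.

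The Statistical Analysis Plan section states that "Intention-to-treat strategy will be used in this study" and that "the secondary outcomes (hospital stay duration, icu stay duration and others) are compared using Kruskal-Wallis or ANOVA test". The choice between the two tests depends only on data type and distribution. No time-to-event or competing-risk method is named, and no section gives a value, rank or censoring rule for a patient who dies.

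Deaths are expected. The Inclusion criteria admit "Moderate, sever or critical COVID-19 disease as defined by WHO". The Exclusion criteria remove only patients expected to die within 48 hours. The first primary outcome is 28-day mortality.

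One primary outcome has a related wording problem. The Outcomes section gives it as "PCR test results at end of hospital visit (efficacy", and the SAP section as "result of PCR test at hospital discharge".

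**The concern.** Intention-to-treat fixes who is analysed. It does not fix what value a patient receives when the outcome cannot be observed. Two gaps follow.

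- **Time to improvement.** A patient who dies without a 2-point reduction or a discharge has no improvement time. Kruskal-Wallis and ANOVA need a number for every patient. Without a rule, the likely default is to analyse those who have one, which means survivors. A difference in mortality then does not show in this outcome. Patients alive but unimproved at day 28 raise the same problem.
- **Hospital and ICU stay.** A patient who dies does have a count of days. If it is used as observed, a death that comes before a typical discharge is recorded as a short stay, which reads as a good result. An arm with more early deaths can look better, and an arm that saves lives can look worse.

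The choice between dropping, keeping and ranking deaths would otherwise be made after the data are seen, and each of these outcomes carries its own P-value.

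**Working it through.** **Inputs from the documents.** Deaths: 360 in three months, or 120 per month (Sample Size). Admissions: 250 per month (Sample Size). Arms: 53, 106 and 106 (Table 2). Planned difference in 28-day mortality: 0.2 (Sample Size). Significance: P ≤ 0.05 (SAP). The plan gives no figure for stay or improvement time, so there is none to reproduce.

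**How common deaths are.** 360 / (3 × 250) = 0.48. This is approximate: the deaths are for August to October 2021, the admissions are a current rate, and both cover all hospitalized patients. At 48%, expected deaths are 53 × 0.48 ≈ 25, 106 × 0.48 ≈ 51 in each comparator arm, and 265 × 0.48 ≈ 127 in total.

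**Direction for hospital stay.** Mean observed stay = p × (mean days to death) + (1 − p) × (mean days to discharge), where p is mortality. All times are assumptions.

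| Days to death / discharge | p = 28% | p = 48% | p = 68% |
|---|---|---|---|
| 5 / 12 | 10.0 | 8.6 | 7.2 |
| 10 / 10 | 10.0 | 10.0 | 10.0 |
| 14 / 10 | 11.1 | 11.9 | 12.7 |

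For example, 0.68 × 5 + 0.32 × 12 = 7.24. Higher mortality shortens the mean stay only if deaths come earlier than discharges.

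**Size for hospital stay.** Simulation of 5,000 trials per setting with 53/106/106 patients and a tie-corrected Kruskal-Wallis test. Assumptions: lognormal stays, log-SD 0.5, survivor median 12 days, no difference among survivors. Cocktail mortality is 68% against 48% in both other arms, the planned 20 points in the adverse direction.

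| Median days to death | Cocktail significantly shorter | Significantly longer |
|---|---|---|
| 6 | 25.2% | 0.1% |
| 8 | 13.0% | 0.4% |
| 10 | 5.1% | 1.2% |
| 12 | 2.2% | 2.8% |
| 16 | 0.8% | 7.8% |

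Chance alone would give about 2.5% on each side. In the plan's intended direction (28% versus 48%), the cocktail is significantly longer in 25.0% and 11.9% at death medians of 6 and 8 days. With deaths ranked worst and stay capped at 28 days, a false benefit at 68% versus 48% occurs in 0.0% and harm is flagged in about 59%. With equal mortality the total error is 4.6–5.8%.

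**Size for time to improvement.** Assumptions: survivor median 10 days, log-SD 0.6, same survivor times in all arms, no improvement before death. At 68% versus 48%, dropping deaths leaves 53 × 0.32 ≈ 17 and 106 × 0.52 ≈ 55 patients per arm. The test is significant in about 5% of trials, both directions combined, which is its false-positive rate. With deaths and non-improvers tied at a value beyond day 28, it is significant in about 55%. At 28% versus 48% the tied-value test detects the benefit in about 52%.

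**PCR.** If the result is taken at discharge and patients who die in hospital have none, about 25 of 53 and 51 of 106 per arm have no primary PCR result at 48% mortality. At an assumed 30%, the figures are 53 × 0.30 ≈ 16 and 106 × 0.30 ≈ 32.

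**The case against.** The best defence is that mortality is itself a primary outcome. At 68% versus 48% it is significant for harm in about 65% of simulated trials, and most false stay benefits fall in those trials. A false stay benefit without a mortality signal occurs in only about 2–3%, against about 2% when mortality is equal. With a 10-point excess (58% versus 48%) it is 3.5–4.0%. This stands. A reader might infer that the plan could pass off a harmful treatment as beneficial; beside a reported mortality comparison, the figures do not support that.

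The stay and improvement times are all assumed, and the 48% is rough. This also stands. The omission is certain, but its effect is not.

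Ranking deaths worst makes stay a near copy of mortality. That is a real cost, and it is why observed days should still be shown. It does not rescue time to improvement, where the plan supplies no value at all.

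Two further inferences are tempting:

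- **"Invasive mechanical ventilation and oxygen support duration (days"**. A reader might expect these durations to be biased towards the arm with more deaths. The direction is not established, because the trial includes moderate disease and the document does not say whether never-ventilated patients count as 0 days or are left out.
- **Laboratory and SOFA values at days 14 and 28.** Their handling after death or discharge is ordinary missing detail, and the laboratory parameters are limited to the hospital stay.

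On PCR, the two phrases may be loose synonyms. They still need one meaning, because the end of a hospital visit can include a last test before death, and discharge may not.

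**Conclusion.** The concern holds for time to clinical improvement and for hospital and ICU stay. It should be corrected, but it does not threaten the primary mortality comparison.

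It is firmest for time to improvement: patients who die unimproved have no value and the named tests cannot censor them. The contrast of about 5% with about 55% assumes identical survivor times and no improvement before death. The low figure follows from those assumptions, and it shows what a survivors-only comparison cannot see.

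For hospital stay the problem is conditional. It arises if observed days are analysed as they stand and if deaths come before a typical discharge. Under the assumed times the misleading result reaches about 25% of trials at a death median of 6 days, disappears at equal medians and reverses at 16 days. ICU stay has the same gap in its rules but was not simulated, so no size or direction is claimed for it.

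The PCR wording is a separate inconsistency in a primary outcome.

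**What to change.** Add to the Statistical Analysis Plan section:

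1. **Time to improvement.** Count discharge only if the patient leaves alive. Give patients who die by day 28 without improvement, and patients not improved by day 28, one tied value beyond day 28. Kruskal-Wallis then still applies. The alternative is cumulative incidence with death as a competing event.
2. **Hospital and ICU stay.** Compare days to day 28 by Kruskal-Wallis, with deaths by day 28 ranked worst. Show observed days by survival status descriptively beside 28-day mortality. For ICU stay, say how survivors never admitted to ICU are counted.
3. **Deaths after improvement or after discharge alive.** State one rule for these patients when they die by day 28, and apply it to both outcomes. Otherwise the same patient could be worst for stay and a success for improvement.

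Separately, give the primary PCR outcome one timing in the Outcomes and SAP sections, and say how in-hospital deaths are counted.

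**Cost.** A few sentences, and no change to design, sample size or tests. The document does not list the electronic CRF fields; dates of discharge, death, improvement and ICU entry and exit are needed, but the planned outcomes largely require them already. The day-28 limit on stay is new. The main downside is that the ranked outcomes become composites driven largely by mortality and no longer read as raw days. Ranked stay gave the same significance verdict as mortality in about 88% of simulated trials at 68% versus 48%, and in about 81–82% at 28% versus 48%.
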